This study will be the first of its kind to utilize blinding and a control while analyzing BoNT-A injections for CECS in the military health system. It will also be the first to judge whether formal gait retraining is required for the successful non-operative treatment of CECS or if BoNT-A injections is sufficient as a stand-alone treatment. The information gained from this study has the potential to revolutionize the treatment of CECS and provide guidance to physicians caring for these patients all over the world.

9.3

Objectives/Specific Aims/Research Questions:

Describe the purpose and objective(s) of the study, specific aims, and/or research questions /hypotheses

The long-term objective of this project is to simultaneously assess the effectiveness of non-surgical treatments, botulinumtoxin A (BoNT-A) injections and supervised gait retraining (SGR), in terms of pain control and ability to return to full duty among adult active duty service members suffering from lower extremity Chronic Exertional Compartment Syndrome (CECS), specifically of the anterior and/or lateral compartments.^{1,2,3}

This study will determine if successful supervised gait retraining is required for the successful non-operative treatment of anterior and/or lateral CECS or if BoNT-A injections is sufficient as a standalone treatment. Furthermore, this study will determine if BoNT-A injections plus supervised gait retraining is better.

Study Treatment Groups:

- Group 1 - Home Based Gait Retraining (HBGR) and Normal Saline (placebo)
- Group 2 - Supervised Gait Retraining (SGR) and Normal Saline (placebo)
- Group 3 - BoNT-A + HBGR
- Group 4 - BoNT-A + SGR

Objective 1: Assess and compare the treatment efficacy of the below study treatment groups.

Hypothesis 1: BoNT-A injections will prove effective as a non-surgical treatment option for CECS.

Process for Hypothesis 1: Evaluate functional improvements in Group 3 as compared to Group 1 via the subjective and objective data variables described in protocol sections 10.1 & 10.2.

Hypothesis 2: Supervised Gait Retraining will prove effective as a non-surgical treatment option for CECS.

Process for Hypothesis 2: Evaluate functional improvements in Group 2 as compared to Group 1 via the subjective and objective data variables described in protocol sections 10.1 & 10.2.

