Chronic exertional compartment syndrome (CECS) may occur in the four compartments of the lower leg: anterior, lateral, superficial posterior, and deep posterior. CECS typically occurs in the anterior and/or lateral compartments and is commonly seen within the military and has been shown to result in both significant warfighter disability and degradation of the unit mission. Active duty military members represent a population with a significantly higher risk of CECS. Military members also face requirements for exercise training and fitness that are jeopardized by a condition that limits aerobic exercise and physical activity. Fasciotomy, the current standard definitive treatment, has significant limitations in terms of effectiveness and direct and indirect costs. Pooled data shows that 28-59% of military members with CECS who underwent fasciotomy were unable to return to full duty and approximately 20% ultimately required medical separation from the military.¹ Not included in these statistics was the loss of member productivity during appointments, procedures, and recovery time.

Given the significant impact of CECS on the military mission, there is strong interest and motivation to investigate less invasive and less costly alternatives to fasciotomy. Within the National Capital Region, military sports medicine physicians have been utilizing both Supervised Gait Retraining (SGR) and botulinumtoxin A (BoNT-A) injections for years. While results have been promising for both options, there is insufficient high-quality data to create treatment guidelines and protocols for other providers in the military who treat these patients.

Based on a retrospective review of 29 patients from Fort Belvoir Community Hospital who received BoNT-A injections for CECS, approximately two-thirds of these patients were able to return to their desired activity level. In addition, among 11 patients who eventually underwent both BoNT-A injections and fasciotomy, only 2 patients would recommend fasciotomy as the first intervention over BoNT-A. Additionally, 69% of the patients in this review expressed satisfaction with BoNT-A injections. Aside from self-limited weakness with ankle dorsiflexion, there were no significant adverse effects.² The next logical step is to study the effect of BoNT-A injections in a randomized, prospective, single-blinded, placebo- controlled fashion.

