Those randomized into the normal saline groups will receive injections in the identical manner above, using the appropriate amount of solution (0.5 mL to 1 mL). The syringes will be prepared by the clinical research staff using standard sterile techniques, out of view of the participant to ensure appropriate blinding.

Study Injection Documentation (both groups):

All injections will be done under ultrasound guidance. The provider will use the ultrasound machine to identify bony landmarks of the tibial plateau and will then move the probe laterally towards the fibular head to identify the anterior and lateral compartments of the lower leg. Distally, the provider will identify the midway area between the fibular head and the tip of the lateral malleolus.

Study injection administration to the participant will be documented using a Treatment Documentation CRF (Appendix N). This Treatment Documentation CRF will be entered into REDCap. Study injection administration will also be documented in the participant's electronic medical record following standard procedures.

Supervised Gait Retraining (SGR):

The SGR course will focus on mid-forefoot strike, increasing their cadence while shortening their stride, and decreasing their peak ground reaction force. This program has been developed by physical therapists at West Point and the Army DPT program in Fort Sam Houston. This program uses group physical therapy sessions, lower extremity exercises, home exercise training drills, and advanced wearable technology to effectively change key gait parameters.

Supervised physical therapy sessions will be documented using a SGR Physical Therapy Documentation CRF (Appendix M). This SGR Physical Therapy Documentation CRF will be entered into REDCap. Study supervised physical therapy sessions will also be documented in the participant's electronic medical record following standard procedures. Participants in the SGR group(s) will also be sent home with a handout (Appendix L) explaining exercises that can/should be done from home to supplement their supervised physical therapy sessions.

Home Based Gait Retraining:

The HBGR will focus on increasing cadence, running softer and increasing endurance strength with exercises for the lower extremity. A handout (Appendix L) explaining desired exercises and gait retraining will be given to each participant with daily exercise instructions. Participants will be contacted weekly as a reminder to complete their home program.

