There will be appropriate data sharing agreements in place between the data owner(s) (e.g., DHA for AHLTA) and the Walter Reed National Military Medical Center (WRNMMC), as well as the Uniformed Services University (USU) and all appropriate parties involved in the handling of data (e.g., The Geneva Foundation).

10.2 Data Collection:

Describe all the data variables, information to be collected, the source of the data, and how the data will be operationally measured.

Please see attached Data Collection Schedule (Appendix H).

The local study team will collect study data directly from the study participant, from their attending provider or, where applicable, from the participant's medical record (i.e., relevant medical and treatment history and relevant clinical notes) and record it on paper CRFs (see Appendixes A-F). Study completion will be documented (see Appendix S). The completed paper CRFs will serve as source documents for this study. Participants may also enter study data directly into REDCap using a coded survey link. In these cases, the completed eCRFs will be printed and stored in the participant's research files and serve as source documents. Other source documents include relevant laboratory results (i.e., hCG urine test) and relevant clinical notes which will be printed, redacted, and stored in the participant's research file.

With the exception of the Informed Consent Form, HIPAA Authorization, and Intake CRF (Appendix B) which collects contact information, all paper CRFs will be identified using a unique study ID only, and not by the participant's name, social security number, DoD ID, or other protected identifier.

The primary outcome will be functional improvement via statistical changes in the Balance Error Scoring System (BESS), University of Wisconsin Running Injury and Recovery Index (UWRI), Single Assessment Numerical Evaluation (SANE), Patient Specific Functional Scale (PSFS), Global Rate of Change (GROC), objective data from the gait and run analyses (e.g., average vertical load rate, cadence, foot pattern strike, etc.), ability to return to full active duty, and ability to complete a 2-mile run. Full active duty is defined as meeting all service specific requirements of physical training and ability to complete work duties with either no pain or pain that is tolerable as determined by the patient.

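### Gait variables that supervised retraining coaches sit inside the primary outcome, so a Group 2 v Group 1 difference on them could be read as efficacy when it shows only that coaching was delivered or followed

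*Combined protocol and SAP*

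**What the plan says.** Section 10.2 opens its outcome definition with "The primary outcome will be functional improvement via statistical changes in the Balance Error Scoring System (BESS" and continues through several patient-reported scores (UWRI, SANE, PSFS, GROC). It then adds "objective data from the gait and run analyses (e.g., average vertical load rate, cadence, foot pattern strike, etc" and finishes with "ability to return to full active duty, and ability to complete a 2-mile run". Pain on the NPRS is a secondary outcome.

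Section 10.1 describes the two retraining programmes. For the supervised one: "The SGR course will focus on mid-forefoot strike, increasing their cadence while shortening their stride, and decreasing their peak ground reaction force". Its tools include "advanced wearable technology to effectively change key gait parameters". For the home programme, which is the comparator: "The HBGR will focus on increasing cadence, running softer and increasing endurance strength with exercises for the lower extremity".

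Section 9.3 gives the process for Hypothesis 2, that SGR is an effective treatment for CECS: "Evaluate functional improvements in Group 2 as compared to Group 1 via the subjective and objective data variables" set out in sections 10.1 and 10.2. Hypotheses 1 and 3 use the same reference to 10.1 and 10.2. Section 11.1 plans a logistic regression with three group indicators and does not name the outcome variable. Section 11.5 bases the sample size on passing the 2-mile run.

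**The concern.** Section 9.2 presents gait change as the route by which retraining lowers compartment pressure and relieves pain. That makes it a mechanism, or a sign that the training was taken up. Section 10.2 nevertheless counts it as functional improvement, on the same footing as running two miles or returning to full duty. A runner can adopt the coached style and remain in pain or unable to run the distance.

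The plan states no hierarchy, no composite rule, no component that must improve, and no threshold or direction for the gait variables. If Group 2 differs from Group 1 in foot strike and in nothing else, the plan contains nothing that would prevent a report that SGR produced functional improvement. Group 4 v Group 3 in Hypothesis 3 is also SGR v HBGR, so the point carries over to it.

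Under BoNT-A the gait variables have a different problem: no section says which change would be a benefit.

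**Working it through.** **1. Match each gait outcome to what each arm is taught (10.2 against 10.1).**

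| Gait outcome in 10.2 | SGR content | HBGR content | Strength of the concern |
|---|---|---|---|
| Foot strike pattern | Mid-forefoot strike, named | Not named | Strongest |
| Cadence | Increase, named | Increase, named | Weaker: both arms coached |
| Average vertical load rate | Lower peak ground reaction force (related, not the same quantity) | Softer running | Weaker: indirect match, both arms coached |

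Supervision and wearable technology as training tools are described only for SGR. Some extra shift under SGR is therefore plausible on all three, but its size is unknown.

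**2. Follow the route from variable to claim.** Section 10.2 makes the variables part of the primary outcome. Section 9.3 judges Hypothesis 2 on the variables of 10.1 and 10.2. Section 11.1 neither names an outcome nor excludes gait. Nothing along this route filters the gait variables out.

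**3. Reproduce the plan's own figure.** Section 11.5 gives 80% power for the SGR effect with 120 patients in total (30 per arm), from 2-mile-run pass rates of 15% (control) and 50% (SGR) at p < 0.05, taken here as two-sided.

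- Pooled rate = (0.15 + 0.50)/2 = 0.325.
- n per arm = [1.96√(2 × 0.325 × 0.675) + 0.842√(0.15 × 0.85 + 0.50 × 0.50)]² / 0.35² = (1.298 + 0.517)² / 0.1225 ≈ 26.9, so 27 per arm, or 108 in total. With continuity correction it is 33 per arm, or 132 in total.
- Power at 30 per arm = Φ[(0.35√30 − 1.298)/0.614] = Φ(1.007) ≈ 84%.
- Simulation of the four-arm logistic model with uniform randomisation (40,000 runs, Wald test) gives 81.8%.

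The figure reproduces. At the planned 480 (120 per arm) the same comparison has power above 99.9%. Hypothesis 2 therefore does not need the gait variables for power.

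**4. Illustrate the size of the problem.** The documents give no SD and no expected shift for any gait variable, so the shifts below are assumptions. The test is a two-sided two-sample comparison of means at 0.05 with 120 per arm. This is not the planned analysis: 11.1 specifies logistic regression, and no gait cut-off is stated. The effect on every patient outcome is set to zero.

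Noncentrality = d√(120/2) = d√60 = 7.746d. Power = Φ(7.746d − 1.96) + Φ(−7.746d − 1.96).

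| Assumed SGR − HBGR shift (SD) | Noncentrality | Chance of p < 0.05 on one gait variable |
|---|---|---|
| 0.1 | 0.775 | 12% |
| 0.2 | 1.549 | 34% |
| 0.3 | 2.324 | 64% |
| 0.5 | 3.873 | 97% |

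The low rows are the more plausible where HBGR teaches the same thing. The high rows are more plausible for something coached in one arm only.

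**The case against.** The best defence is that Group 1 is also coached. HBGR teaches cadence and softer running, supplies a handout and makes weekly contact, so the contrast on those items may be small. This stands, and it is why the point rests mainly on foot strike.

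A second defence is that no section says significance on one listed variable satisfies Hypothesis 2, and that the only endpoint given success rates and power is the 2-mile run. This stands in part. The sample-size section suggests the run may be meant to decide, but no section says so, and 10.2 and 9.3 read otherwise.

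A third is that gait change is a reasonable objective companion to subjective scores, being the proposed mechanism. That supports collecting and reporting it. It does not support counting it as functional improvement.

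A reader might infer more than the documents support:

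- *That Hypothesis 2 would be declared met on gait alone.* There is no decision rule, so the most that can be said is that nothing prevents that reading.
- *That BoNT-A weakness would be scored as improved foot strike.* Section 9.6 does report "Aside from self-limited weakness with ankle dorsiflexion, there were no significant adverse effects", but no section links this to foot strike. Section 9.2 describes the weakness in another series as transient and without functional consequence. What stands is only that no direction of benefit is stated.
- *That participants who do not strike rearfoot at entry bias the comparison.* They dilute the foot-strike item, but under randomisation they do not by themselves bias it.

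**Conclusion.** The concern holds in this form: the primary outcome includes running habits that SGR coaches, and the plan lets a between-arm difference on them stand as evidence of effectiveness. It is firm for foot strike, weaker for cadence, and indirect for load rate. The absence of a stated direction of benefit under BoNT-A is a secondary gap.

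The size cannot be fixed from the documents. On assumed shifts of 0.1 to 0.5 SD, the chance of a significant gait result without any functional benefit runs from about 12% to 97% for one variable. These figures rest on a two-sample comparison of means with 120 evaluable patients per arm. They show that the planned sample is large enough for a moderate coaching effect to reach significance; they do not predict that it will.

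**What to change.** Two linked edits are needed.

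1. **Section 10.2:** move the gait and run-analysis variables, including the open-ended remainder of that list, out of the primary outcome. List them as mechanistic or adherence measures reported by arm.
2. **Section 9.3:** amend the process text for Hypotheses 1 to 3 so that effectiveness is judged on the remaining functional outcomes (2-mile run, return to full duty, UWRI, SANE and PSFS, with BESS and GROC left as they are) and not on the gait variables. Editing 10.2 alone would not be enough, because 9.3 refers to all the variables of 10.1 and 10.2.

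The cost is that gait change can no longer be claimed as primary efficacy. Data collection, the gait analysis described in 10.14 and the sample size are unchanged. The edits do not supply a hierarchy or decision rule for the remaining primary measures, which still has to be stated separately.

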Hypothesis 3: The use of both BoNT-A injections and supervised gait retraining will be more effective than either treatment alone. In adult active duty service members with CECS, the use of both BoNT-A injections and supervised gait retraining returns service members to full duty, including being able to complete their service-specific military physical tests, sooner and for sustained longer periods than SGR or BoNT-A injections alone.

Process for Hypothesis 3: Evaluate functional improvements in Group 4 as compared to Groups 2 & 3 via the subjective and objective data variables described in protocol sections 10.1 & 10.2. Assess the ability of all study groups to complete a 2-mile run and to compete their required service-specific physical fitness testing within the established standards at 8 weeks, 3 months, 6 months, and 12 months post-study injection.

9.4 Study Design:

Describe study design in one to two sentences (e.g., prospective, use of existing records/data /specimens, observational, cross-sectional, interventional, randomized, placebo-controlled, cohort, etc.). Specify the phase – Phase I, II, III, or IV – for FDA-regulated investigational drug research

Multi-site, single-blinded randomized placebo-controlled study

9.5 Target Population:

Describe the population to whom the study findings will be generalized

Adult military beneficiaries diagnosed with Chronic Exertional Compartment Syndrome (CECS)

9.6 Benefit to the DoD:

State how this study will impact or be of benefit to the Department of Defense

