The Informed Consent Form for this research study states that de-identified research data will be shared with the MIRROR/USU and maintained indefinitely for possible use in future research. By consenting for this research study, participants agree to allow us to maintain their de-identified research data indefinitely for possible use in future research.

Data Withdrawal:

Because there will be no way to link an individual's identity to their specific research data, participants will not be able to withdraw their de-identified research data from storage.

Is this a data repository?

☒ Yes ☐ No

If Yes, provide the name of the Repository

USU OCIO REDCap

Who will have access to the Repository?

MIRROR core team, investigators, study team members, as applicable.

Access to the de-identified research data will be governed strictly on an individual-by-individual basis within the secure electronic data capture and management system. Individual data access as well as privileges will be clearly delegated, audited, and monitored by MIRROR/USU.

What data type will be stored in the Repository?

- ☐ Protected Health Information
- ☐ Limited Data Set
- ☒ De-identified Data

11.0

Statistical/Data Analysis Plan

11.1 Data Analysis Plan and Statistical Considerations:

List the statistical methods to be used to address the primary and secondary objectives, specific aims, and/or research hypotheses. Explain how missing data and outliers will be handled in the analysis. The analysis plan should be consistent with the study objectives. Include any subgroup analyses (e.g., gender or age group). Specify statistical methods and variables for each analysis. Describe how confounding variables will be controlled in the data analysis.

To maximize efficiency of the factorial study design, the clinical effectiveness of each treatment will be measured simultaneously using logistic regression analysis. Specifically, the regression model will include three binary independent variables, one for each treatment group, with group 1 (HBGR + NS) as the reference treatment. In this way, the group 3 coefficient (BoNT-A + HBGR) will correspond to the effect estimate of group 3 vs 1 (specific aim 1), the group 2 coefficient (SGR + NS) will correspond to the effect estimate of group 2 vs 1 (specific aim 2), and the group 4 coefficient (BoNT-A + SGR) will correspond to the effect estimate of group 4 vs either 2 or 3 (specific aim 3).

Missing Data and Outliers:

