11.5 Please provide a justification for your sample size

Using a 2x2 factorial design and assuming success rates for passing the US Army 2-mile run test among control (saline/home based gait retraining), botulinumtoxin A (BoNT-A) injection, supervised gait retraining (SGR), and combined therapy (BoNT-A + SGR), respectively, are 15%, 80%, 50%, and 85%, we estimate that enrolling a grand total of at least 60 patients would yield 80% power to detect the effect of BoNT-A, enrolling a grand total of at least 120 patients would yield 80% power to detect the effect of SGR, and enrolling a grand total of at least 380 patients would yield 80% power to demonstrate the benefit of combined therapy (BoNT-A + SGR) vs. either therapy in isolation. If we can obtain complete data on more than 380 participants, then it will strengthen our power. We hope to have a final sample of 480 participants. Assuming roughly 20% attrition and accounting for screen failures, we are requesting to enroll up to 620 participants across all performance sites.

Power was estimated using Monte Carlo simulations assuming uniform randomization among four groups in the 2x2 factorial design, while testing for statistical significance simultaneously among the four groups of control, BoNT-A, SGR, and combined therapy using a generalized linear model. Statistical significance was indicated if the corresponding $p < 0.05$ per generalized linear model.

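### Section 11.1 tests the combination against control, not against each single treatment: with group 1 as reference, the group 4 coefficient estimates group 4 vs group 1

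*Combined protocol and SAP*

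**What the plan says.** Section 11.1 describes a logistic regression in which "the regression model will include three binary independent variables, one for each treatment group, with group 1 (HBGR + NS) as the reference treatment". It then gives a meaning to each coefficient. For aim 1, "the group 3 coefficient (BoNT-A + HBGR) will correspond to the effect estimate of group 3 vs 1 (specific aim 1"), and the group 2 coefficient is read in the same way as group 2 vs group 1. For aim 3, "the group 4 coefficient (BoNT-A + SGR) will correspond to the effect estimate of group 4 vs either 2 or 3 (specific aim 3"). The section gives no linear contrast, no second fit with another reference group, and no rule for combining two comparisons.

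Section 9.3 states Hypothesis 3 as "The use of both BoNT-A injections and supervised gait retraining will be more effective than either treatment alone", and its process is to "Evaluate functional improvements in Group 4 as compared to Groups 2 & 3".

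Section 11.5 assumes 2-mile-run success of 15% (control), 80% (BoNT-A), 50% (SGR) and 85% (both). It says that "enrolling a grand total of at least 380 patients would yield 80% power to demonstrate the benefit of combined therapy" over either treatment alone. In the power simulation, significance meant p < 0.05 in a generalized linear model.

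**The concern.** The reading of the group 4 coefficient contradicts the coding in the same paragraph. With group 1 as reference, every coefficient is a log odds ratio against group 1; section 11.1 follows this for groups 2 and 3 and departs from it for group 4. Nor can one coefficient stand for two comparisons unless groups 2 and 3 have equal success rates, and section 11.5 assumes 50% and 80%.

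At stake is the claim that the combination beats each component. A comparison with control carries no information on whether adding SGR to BoNT-A, or BoNT-A to SGR, achieves anything. If one treatment works and the other contributes nothing, the coefficient will still usually be significant. It would then be reported as support for giving both.

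**Working it through.** **Inputs.** Success rates from section 11.5: p1 = 0.15 (control), p2 = 0.50 (SGR), p3 = 0.80 (BoNT-A), p4 = 0.85 (both). Equal allocation: 95 per group at 380 and 120 per group at 480 (sections 11.2 and 11.5). Two-sided 0.05 is assumed, because the documents do not state sidedness.

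**What the coefficient estimates.** The model is logit(p) = b0 + b2·G2 + b3·G3 + b4·G4, with b0 = logit(p1). Hence:

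- b4 = logit(0.85) − logit(0.15) = 1.735 + 1.735 = 3.469, OR 32.1 (group 4 vs 1)
- b4 − b3 = logit(0.85) − logit(0.80) = 1.735 − 1.386 = 0.348, OR 1.42 (group 4 vs 3)
- b4 − b2 = logit(0.85) − logit(0.50) = 1.735 − 0 = 1.735, OR 5.67 (group 4 vs 2)

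**The plan's own sample sizes.** A Wald test of group 2 vs 1 at 120 in total (30 per group) has about 82% power, in line with section 11.5. For group 3 vs 1 at 60 in total, power runs from about 74% to 97%, depending on the test, on the allocation, and on how samples with an empty cell are treated; the stated 80% lies in that range. The 380 figure is not reproduced by any comparison that Hypothesis 3 could mean: at 95 per group, 4 vs 1 and 4 vs 2 each have about 100% power, and 4 vs 3 about 14%. The nearest match is the BoNT-A by SGR interaction, at 75% (logit) or 81% (probit). At the assumed rates that interaction is negative: 1.735 − 1.386 − 0 + (−1.735) = −1.386. It therefore does not show a benefit of combining.

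**How often b4 is significant when the combination adds nothing.** For groups i and j with n each, SE = √[1/(n·pi·qi) + 1/(n·pj·qj)], with q = 1 − p, and power ≈ Φ(|log OR|/SE − 1.96). At n = 120 and p1 = 0.15:

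| Group 4, equal to the best single treatment | log OR vs group 1 | SE | Formula | Simulation or exact calculation |
|---|---|---|---|---|
| 80% | 3.121 | 0.343 | about 100% | about 100% |
| 30% | 0.887 | 0.324 | 78% | about 80% |
| 25% | 0.636 | 0.331 | 48% | about 49% |
| 20% | 0.348 | 0.343 | 17% | about 17% |
| 15% (no better than control) | 0 | – | 5% | about 5% |

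In the first row group 2 is at 50%; in the others all active groups share the rate shown. If group 4 were at 50% and BoNT-A alone at 80%, so that the combination was worse than one component, b4 would still be significant in about 100% of trials.

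**The contrasts that Hypothesis 3 needs.** When group 4 equals BoNT-A alone at 80%, b4 − b3 is significant in favour of group 4 in about 2.4% of trials at 480, and so is the joint requirement. Under a rule satisfied by either contrast, b4 − b2 alone would succeed in more than 99%.

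**Power of the correct joint test at 85% vs 80%.**

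- n = 95: SE = √[1/(95 × 0.1275) + 1/(95 × 0.16)] = 0.385; Φ(0.348/0.385 − 1.96) = Φ(−1.06) ≈ 14–15%; simulation gives about 14%.
- n = 120: SE = 0.343; Φ(1.016 − 1.96) = Φ(−0.94) ≈ 17%; simulation gives 17%.

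The 4 vs 2 contrast has about 100% power at both sizes, so 4 vs 3 alone sets the joint power. For 80% power on 4 vs 3, n = [1.96·√(2 × 0.825 × 0.175) + 0.842·√(0.16 + 0.1275)]² / 0.05² ≈ 906 per group, or 4 × 906 = 3,624 in total.

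**The case against.** Section 9.3 names the right comparison, section 11.1 calls the coefficient an effect estimate and attaches no significance rule to it, and the only p < 0.05 criterion is in the description of the power simulation. A careful analyst could take both contrasts from the fitted model. This stands as a limit on the consequence: a false claim is a risk if section 11.1 is followed, not a certainty. It does not rescue the text, because the documents then conflict on aim 3, and the contrast and decision rule would be chosen outside the plan.

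The repeated reference to a factorial design, and the near match of 380 to an interaction test, suggest that factor coding may have been used in the simulation. They do not prove it. The third coefficient would then be the interaction, which is also neither 4 vs 2 nor 4 vs 3. The rejection rates above apply only to the coding that section 11.1 states.

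A reader might infer that any benefit of BoNT-A over control makes the coefficient significant. The plan does not support that. The coefficient depends on group 4's rate, not group 3's, and on the size of the difference: rejection is about 49% at 25% vs 15%, about 17% at 20% vs 15%, and about 5% if group 4 equals control, however well BoNT-A alone performs.

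**Conclusion.** The interpretation in section 11.1 is wrong as a matter of algebra and needs correcting before analysis. The coefficient assigned to aim 3 is an odds ratio of 32.1 against control at the plan's rates, where the hypothesis concerns 1.42 and 5.67. Used as the test, it would support the combination in about 100% of trials under the plan's assumed 80% for BoNT-A even if SGR added nothing to it, and less often when effects over control are smaller. These rates assume that the section 11.1 coding is followed, that the coefficient is tested at two-sided 0.05, and that 480 participants are evaluable.

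It would go too far to say that the trial will declare Hypothesis 3 proven regardless: that requires both use of the mislabelled coefficient and a sizeable advantage of group 4 over control. The correct test also exposes a second problem. At 85% vs 80%, neither 380 nor 480 participants gives anything near the 80% power that section 11.5 claims for this aim.

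**What to change.** In section 11.1, replace the reading of the group 4 coefficient. For the binary 2-mile-run outcome at one named time point, define aim 3 as two contrasts from the same model, b4 − b3 and b4 − b2. Claim that the combination beats each single treatment only if both are significant in favour of group 4 at two-sided 0.05. Because both must succeed, this joint claim on that one outcome and time point needs no further adjustment. The group 3 and group 2 coefficients keep their roles for aims 1 and 2.

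The model and data collection do not change, and the edit to section 11.1 is short. The cost falls on section 11.5, where the 80% power at 380 must be withdrawn or restated: about 14% at 380 and 17% at 480 under the current rates. The sponsor then has to accept low power for aim 3, justify a larger difference, or describe that comparison as estimation with confidence intervals. At 120 per group, 80% power would need about 92% in group 4 against 80% in group 3.

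The two contrasts do not cover the rest of Hypothesis 3 (earlier and longer-lasting return to duty) or the non-binary primary outcomes in section 10.2. Those need their own analyses and a statement on multiplicity.
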